8.7 Publication of Results

All data generated as a result of this study will be regarded as confidential, until appropriate analysis and review by the Sponsor or its designee are completed. The results of the study may be published or presented by the Investigator(s) after the review by, and in consultation and agreement with the Sponsor, and such that confidential or proprietary information is not disclosed.

Prior to publication or presentation, a copy of the final text should be forwarded by the Investigator(s) to the Sponsor or its designee, for comment. Such comments shall aim to ensure the scientific integrity of the proposed publications and/or presentations and ensure that the data and material referring to STAAR Surgical products and activities receive fair, accurate, and reasonable presentation.

APPENDIX A: SCHEDULE OF VISITS AND PARAMETERS

All study tasks should be performed by qualified study site personnel as indicated on the DOA log under the supervision of the PI.

Table 2: Preoperative, Surgical Assessments, and Postoperative Assessments (for each implanted eye)

Note: Postoperative visits for both eyes may be scheduled on the same day only if the study visit window for each eye allows.

[figure not shown]
PROCEDURE/ ASSESSMENTS	PreOp ^{&} Day -120 to Day -1		Op Day 0	V1 Day 1	V2 Day 5-9	V3 Day 21-35	V4 Day 70-98	V5 Day 147-182	V6 Day 330-420	V7 Day 690-810	V8 Day 1050-1170
Demographics/ Medical and Ocular History	X										
UDVA	X	X ^a		X	X	X	X	X	X	X	X
CDVA	X	X ^a			X	X	X	X	X	X	X
Manifest Refraction	X	X ^a			X	X	X	X	X	X	X
Keratometry	X										
Gonioscopy	X							X	X	X	X
Slit Lamp Examination	X			X	X	X	X	X	X	X	X
Crystalline Lens Status	X*					X*	X*	X*	X*	X*	X*
Specular Microscopy (CECC [@])	X							X	X	X	X
[@] AL, ACD, WTW, pupil size, corneal topography	X										
IOP	X		X	X	X	X	X	X	X	X	X
Dilated Fundus Exam	X					X			X	X	X
Cycloplegic Refraction	X										
████████████████████	█										
██████	█										
Lens Vault [§] (via OCT)						X	X	X	X	X	X
ConMeds/AEs	X		X	X	X	X	X	X	X	X	X

^aContact lens wearers only-see Appendix B of study protocol.

[&]Subject must provide informed consent to participate in study prior to undergoing any study specific procedures

* Assign LOCS III grade (see Appendix C). If lens opacity observed, obtain photograph at this visit and each subsequent visit

[@]CECC: corneal endothelial cell count; AL: axial length; WTW: white to white

[§]distance between the posterior surface of the phakic IOL and the anterior surface of the natural crystalline lens

APPENDIX B: INSTRUCTIONS FOR USE

STAAR Surgical EVO/EVO+ Visian® Implantable Collamer® Lens for Myopia, and EVO/EVO+ Visian® Toric Implantable Collamer® Lens for Myopia with Astigmatism Investigational Devices (EVO/EVO+ lenses)

Study CP19-01: INSTRUCTIONS FOR USE

Manufacturer:

STAAR Surgical Company
[name]
[name]
USA

[contact]
[contact]

CAUTION – Investigational Device. Limited by Federal (or United States) law to investigational use

INDICATIONS

The **EVO/EVO+ ICL for myopia** is indicated for use in patients 21-45 years of age:

1. for the correction of myopia ranging from -3.0 D to \leq -15.0 D spherical equivalent (SE) in the spectacle plane, with less than or equal to 2.5 D of astigmatism (in the spectacle plane);
2. for the reduction of myopia ranging from greater than -15.0 D to -20.0 D SE (in the spectacle plane), with less than or equal to 2.5 D of astigmatism (in the spectacle plane);
3. with an anterior chamber depth (ACD) of 3.00 mm or greater, when measured from the corneal endothelium to the anterior surface of the crystalline lens, and a stable refractive history (within 0.5 D for 1 year prior to implantation).
4. The ICL is intended for placement in the posterior chamber (ciliary sulcus) of the phakic eye.

The ICL functions as a refractive element to optically reduce moderate to high myopia.

The **EVO/EVO+ Toric ICL for myopia with astigmatism** is indicated for use in patients 21-45 years of age:

1. for the correction of myopic astigmatism with spherical equivalent ranging from -3.0 D to \leq -15.0 D (in the spectacle plane) with cylinder (spectacle plane) of 1.0 D to 4.0 D.

2. for the reduction of myopic astigmatism with spherical equivalent ranging from greater than -15.0 D to -20.0 D (in the spectacle plane) with cylinder (spectacle plane) 1.0 D to 4.0 D.
3. with an anterior chamber depth (ACD) of 3.00 mm or greater, when measured from the corneal endothelium to the anterior surface of the crystalline lens and a stable refractive history (within 0.5 D for both spherical equivalent and cylinder for 1 year prior to implantation).
4. The Toric ICL is intended for placement in the posterior chamber (ciliary sulcus) of the phakic eye.

The Toric ICL functions as a refractive element to optically reduce moderate to high myopia with astigmatism.

CONTRAINDICATIONS AND EXCLUSION CRITERIA

- Younger than 21 or older than 45 years of age.
- With true ACD < 3.00 mm*.
- Anterior chamber angle less than Grade III as determined by gonioscopic examination.
- Do not meet the minimum ECD as defined in the “Minimum ECD for Age and True ACD*” table below.
- Unstable or worsening nearsightedness.
- Coefficient of variation of endothelial cell area of > 0.45.
- Percent hexagonality of endothelial cell shape \leq 45 %.
- Difference between cycloplegic refraction spherical equivalent (CRSE) and manifest refraction spherical equivalent (MRSE) of > 0.75 D.
- Ocular hypertension or glaucoma.
- Pseudoexfoliation.
- Pigment dispersion.
- History or clinical signs of iritis/uveitis.
- Insulin-dependent diabetes or diabetic retinopathy.
- History of previous ocular surgery.
- Cataract of any grade.
- Progressive sight threatening disease or other previous or current ocular conditions, other than myopia or myopic degeneration, which may predispose for future complication in either eye.
- Serious, acute, chronic or systemic, non-ophthalmic disease or illness that would increase the operative risk, confound the outcome(s) of the study or which may

preclude study completion (e.g., immunocompromised, connective tissue disease, clinically significant atopic disease, uncontrolled diabetes, etc.).

- Monocular subjects.
- For EVO/EVO+ ICL for myopia: myopia less than -3.00 D SE (in the spectacle plane) or greater than -20.00 D SE (in the spectacle plane) and/or with greater than 2.50 D of astigmatism (in the spectacle plane).
- For EVO/EVO+ Toric ICL for myopia with astigmatism: myopia less than -3.00 D or greater than -20.00 D SE (in the spectacle plane) and/or refractive cylinder (in spectacle plane) less than 1.00 D and greater than 4.00 D.
- Pregnant or nursing women, or those who plan to become pregnant over the course of this clinical study or has another condition with associated fluctuation of hormones that could lead to refractive changes.
- Involved in another clinical study or who may have been involved in a different clinical study within 30 days prior to this clinical study or will be involved in a different clinical study while participating in this study.
- Subjects who, in the judgment of the Investigator, present any emotional, physiologic, or anatomical condition which may preclude participation in this study or provide an inappropriate landscape for the intended study treatment.

Minimum Endothelial Cell Density for Age and True ACD*

Age	Minimum ECD ACD ≥ 3.0 mm	Minimum ECD ACD ≥ 3.2 mm	Minimum ECD ACD ≥ 3.5 mm
21-25	3875 cells/mm ²	3800 cells/mm ²	3250 cells/mm ²
26-30	3425 cells/mm ²	3375 cells/mm ²	2900 cells/mm ²
31-35	3025 cells/mm ²	2975 cells/mm ²	2625 cells/mm ²
36-40	2675 cells/mm ²	2625 cells/mm ²	2350 cells/mm ²
41-45	2350 cells/mm ²	2325 cells/mm ²	2100 cells/mm ²
>45	2075 cells/mm ²	2050 cells/mm ²	1900 cells/mm ²

*The true ACD is defined as the distance from the apex of the posterior corneal surface to the apex of the anterior crystalline lens surface. Many measuring devices provide an ACD measurement defined as the distance from the apex of the anterior corneal surface to the apex of the anterior crystalline lens surface. If the surgeon is using an instrument that measures from the anterior corneal surface, the thickness of the cornea must be subtracted to get the true ACD.

WARNINGS

- Some subjects in the STAAR ICL for Myopia Clinical Study demonstrated endothelial cell loss >30% (range, 30.9% to 42.6%) at 5-7 years postoperatively. The longer-term effects (beyond 5 – 7 years) on the corneal endothelium have not been established. Subjects should be advised about the potential risk of corneal edema, possibly requiring corneal transplantation. ECD should be monitored periodically as long as the ICL remains implanted in the eye(s).

- Secondary to implantation of the ICL, subjects may have increased risk of development of cataract, including visually significant cataract that continues to increase with each year. Implanted eyes should be monitored for cataract periodically as part of normal standard of care for ICL subjects. The long-term risk of visually significant cataract and related secondary surgery may be higher in older subjects and those with higher myopia. The long-term rate (beyond 5-7 years) of cataract formation secondary to implantation, removal and/or replacement of the ICL is unknown.
- Implantation of the ICL is associated with an elevated risk of early postoperative increase in intraocular pressure (IOP; usually associated with pupillary block) that requires secondary surgical intervention. The long-term risks of glaucoma, peripheral anterior synechiae and pigment dispersion are not well established.
- Do not attempt to resterilize or repackage the ICL.
- Do not autoclave the ICL. Do not expose to temperature greater than 40°C. Do not freeze. If temperature requirements are not met, return the ICL to STAAR Surgical as instructed by the study monitor.
- The iridocorneal angle distance may decrease after implantation of the ICL. Iridocorneal angle should be assessed 1 week after implantation and monitored if the angle is extremely narrow.
- A subject with mesopic pupil size that is greater than the optic diameter of the ICL may experience symptoms of glare and/or halos. Subjects should be advised about this potential risk prior to ICL implantation.
- Complete removal of viscoelastic from the eye after completion of the surgical procedure is essential. STAAR Surgical will provide a low molecular weight 2% hydroxypropyl methylcellulose (HPMC) ophthalmic viscosurgical device (OVD) for use in the study.

NOTE: The primary OVD used with the MICL/TMICL during the FDA clinical trials was a low molecular weight 2% HPMC preparation. Short chain sodium hyaluronate acids (viscoelastics) are not to be used in the study due to increased risk of cataract formation related to trapped viscoelastic.

PRECAUTIONS

Prior to surgery, the Investigator must provide prospective subjects with a copy of the study informed consent form and patient information booklet for the predicate product approved in the US and inform subjects of the possible benefits and complications associated with the use of this device.

- Subjects with higher degrees of myopia or myopic astigmatism may experience lower efficacy and higher rates of adverse events (AEs) and complications.
- Inadequate flushing of the viscoelastic from the eye may lead to IOP spikes. IOP will be checked at 1-6 hours after surgery at the Op Visit and at the 1 day postoperative visit.
- The effectiveness of ultraviolet (UV) absorbing intraocular lenses (IOLs) in reducing the incidence of retinal disorders has not been established.

- The relationship between the ICL and retinal detachment is undetermined.

ADVERSE EVENTS

All ocular AEs (only eyes implanted with study lenses) and all serious AEs (both ocular and non-ocular) will be reported in this study. The collection of AEs begins at the time the subject completes the informed consent process to participate in the study.

Adverse events that have been associated with the ICL platform include:

- anterior subcapsular opacities or clinically significant cataracts,
- narrowing of the anterior chamber angle,
- increased IOP,
- pupillary block,
- glaucoma,
- corneal endothelial cell loss,
- loss of CDVA,
- increase in refractive astigmatism,
- pigment dispersion,
- iris transillumination defects.

In addition, ocular AEs associated with the ICL platform may require a secondary surgery in the implanted eye(s). The following surgeries have been associated with the ICL platform:

- surgery to exchange, remove or reposition the lens,
- vitreous aspiration,
- iridotomy/iridectomy for pupillary block,
- wound leak repair,
- retinal detachment repair,
- corneal transplantation.

Experience with intraocular surgery and the implantation of IOLs has shown that some events can be considered normal or expected events after these procedures. Early, low grade anterior chamber cell/flare, corneal edema, and increase in IOP can often be considered normal or expected after phakic IOL surgery. They do not need to be reported as AEs if they occur prior to 1 week postoperatively and if they meet the following criteria:

- AC cells or flare of grade 2 (using the Standardization of Uveitis Nomenclature, SUN criteria¹⁰) or less that require no change in standard postoperative medication regimen; if persisting to 1 week or more these **should** be reported as an AE.
- Corneal edema of \leq grade 2 that does not reduce CDVA to 20/40 or worse and does not require any change in standard postoperative medication regimen; if corneal edema persists to 1 week or more it **should** be reported as an AE.
- Increased IOP that is <10 mmHg above baseline or is <25 mmHg and requires no change in standard postoperative medication regimen or any other special treatment;

increased IOP ≥ 10 mmHg above baseline to a minimum of 25 mmHg at one week or later **should** be reported as an AE.

- Loss of CDVA ≥ 10 letters up to 1 week postoperatively; loss of CDVA ≥ 10 letters at any time point > 1 week postoperatively **should** be reported as an AE.
- All other untoward events that occur during the study, and all events that have sequelae **should** be reported as AEs, regardless of when they occur.

All ocular AEs that fall outside of the above definitions should still be reported as AEs.

SURGICAL INFORMATION

Implantation of the study lenses should only be attempted by a surgeon who has completed the STAAR Surgical Visian ICL Physician Certification Program. Only subjects who have provided written informed consent and meet all eligibility criteria listed in the study protocol can receive investigational lenses in Study CP19-01.

Calculation of Lens Power and Size

The lens power and size calculation for all eyes to receive EVO/EVO+ lenses will be performed by the surgeon using the STAAR Visian ICL Online Calculation and Ordering Software (www.ocos.STAAR.com). Postoperative target for all enrolled eyes will be emmetropia with an acceptable variation of ± 0.50 D spherical equivalent (SE), at the Investigator's discretion. Investigators must use the lens diameter recommended by OCOS.

In the case of an EVO/EVO+ Toric ICL, OCOS will provide the surgeon a cylinder power and a range of spherical powers along with their expected postoperative values (i.e., residual sphere, cylinder, axis and spherical equivalent). An Implantation Orientation Diagram (IOD) will be generated for each study lens identifying the amount and direction of rotation required of the lens after insertion in the eye to provide optimal alignment.

IMPORTANT

Preoperative YAG iridotomies are NOT to be performed with the lenses to be implanted in this study.

Perioperative Medications

The following medication regimen will be followed by all sites:

[figure not shown]
- Topical 4th generation fluoroquinolone QID starting 3 days prior to surgery for a total of 10 days.
- Topical NSAID QID, BID or QD per NSAID labeled dosing instructions for postoperative inflammation starting 3 days prior to surgery for a total of 10 days and then tapered weekly through 28 days after surgery.

- Topical steroid QID starting 3 days prior to surgery for a total of 10 days and then tapered weekly through 28 days after surgery.

Note: No prophylactic systemic or topical IOP lowering medications (e.g., acetazolamide) will be used.

Preoperative Procedures

- The subject will be prepared for surgery according to the surgeon's standard of care for STAAR Visian MICTL/TMISTL surgery.
- Examine the package for correct lens model, dioptric and cylinder power and overall diameter.
- ***EVO/EVO+ Toric ICLs Only:*** As part of the implantation procedure, the lens may need to be rotated up to 22.5 degrees clockwise or counterclockwise from the 0°-180° meridian in order to align the lens axis at the preoperative plus cylinder axis. The surgeon should mark the horizontal axis (0°-180°) of the eye at the slit lamp prior to surgery. These horizontal axis marks will be used as reference points to mark the desired orientation of the lens under the operating microscope, using a suitable corneal axis marking device. For example, if the preoperative plus cylinder axis is at 136° and the lens selected has the cylinder axis at 115°, the lens will need to be rotated 21° counterclockwise from the temporal meridian in eye. In this case the desired axis marked on the cornea would be 21° counterclockwise from the 0°-180° meridian. The online ordering software for the toric ICL is designed to generate an IOD to guide the surgeon in determining the amount and direction of rotation for the specific lens selected. See example below:

Intraoperative Procedures

Preparation of the lenses for use

Perform the following steps in a sterile field.

- Inspect the lens vial. Ensure that it is not damaged or opened. Do not use if the vial is opened or damaged.
- Peel the Tyvek lid stock from the tray, then transfer the vial into the operating field.
- While keeping the vial in a vertical position, remove the aluminum seal and remove the cap.
- Carefully remove the lens from the vial. Handle the lens by the haptic portion. Do not grasp the optic with forceps as this could potentially lead to damage to the smooth anterior and posterior optical surfaces.
- Examine the lens carefully under the microscope for damage or particulate matter.
- Do not allow the ICL to dry after removal from the glass vial. It is recommended that the ICL be held in sterile BSS solution prior to implantation. It should not be exposed to any solutions other than the normally used intraocular irrigating solutions (e.g., isotonic saline, BSS, viscoelastic, etc.)

Delivery System

The lenses will be delivered using the provided MICROSTAAR® Injectors, Model MSI-TF (twist) or MSI-PF (push) with SFC-45 or SFC-45 FP Cartridge. Lenses will be loaded and delivered according to the surgeon's standard of care for STAAR Visian MICL/TMICL surgery.

CAUTION

The ICL should be injected within 1-2 minutes after loading. Viscoelastic materials tend to lose their lubricity if exposed to air too long.

Viscoelastic Usage

STAAR Surgical will provide 2% HPMC OVD for use in this study. Complete removal of OVD from the eye after completion of the surgical procedure is essential.

Do not use short chain OVDs due to increased risk of cataract formation related to trapped viscoelastic.

Surgical Procedures

- 1) Loading the cartridge
 - a. Insert the foam-tipped plunger and holder into the injector, base first.
 - b. The vertical tab of the holder is not intended to be snap locked into the notch of the injector.
 - c. Keeping the plunger and holder in place, advance the injector cap until the ball end of the plunger interlocks with the injector.
 - d. A click can be felt and heard when the plunger is properly secured.
 - e. Retract the plunger fully. The foam-tipped plunger will remain locked in place.

- f. Remove the holder by sliding it back out of the front of the injector.
 - g. Place the assembled foam-tipped plunger and injector into BSS, making sure that the tip of the injector and foam-tipped plunger are completely submerged.
 - h. Hydrate the foam tip plunger. Ensure adequate hydration of the foam tip plunger. If not properly hydrated, the foam tip plunger becomes dehydrated and compressed. In this case, the lens may become trapped between the cartridge and the foam.
 - i. Remove the cartridge from the package.
 - j. Add BSS to the cartridge.
 - k. Add low molecular weight 2% HPMC viscoelastic after BSS.
 - l. Grasp the lens haptic with forceps and place in cartridge loading area. Do not touch the optic of the lens.
 - m. Tuck one long edge and then the other long edge of the lens under the rails, ensuring proper orientation of the lens in the cartridge.
 - n. Close the jaws of the loading forceps and insert them into the barrel, from the front of the cartridge.
 - o. Advance the forceps through the cartridge until the jaws are about to contact the leading edge of the lens.
 - p. Open the jaws of the forceps and grasp the footplate of the lens so that the positioning mark is aligned with the jaws.
 - q. Slowly pull the lens into the barrel while moving the cartridge in the opposite direction.
 - r. Continue this process until the leading edge of the lens is adjacent to the end of the cartridge.
 - s. Release the lens from the forceps.
 - t. Insert the cartridge into the injector and lock into place.
 - u. Observe the lens for proper orientation in the cartridge.
 - v. The lens should be injected within 1 to 2 minutes after loading.
- 2) Marking the axis (toric lens only)
- a. Using the horizontal axis marks placed preoperatively, mark the desired orientation of the lens under the operating microscope, using a suitable corneal axis marking device.

- 3) Constructing the incisions
 - a. Construct one or two paracentesis incisions, 60 – 120 degrees away from the intended location of the temporal clear corneal main incision.
 - b. Inject 2% HPMC viscoelastic into the anterior chamber; do not overfill.
 - c. Construct a temporal clear corneal incision of approximately 3.5 mm or less in width, parallel to the iris plane, with a tunnel length of approximately 1.5 to 1.75 mm.
- 4) Inserting the lens
 - a. Place the tip of the cartridge just inside the clear corneal incision.
 - b. Inject slowly until the “leading right” orientation marking is visible.
 - c. Continue to inject slowly, maintaining the proper orientation of the lens by rotating the cartridge as necessary, until the lens is released from the cartridge.
 - d. Withdraw the cartridge from the incision.
- 5) Positioning the lens
 - a. Inject additional viscoelastic, if needed, anterior to the lens.
 - b. Use a manipulator to sequentially position the footplates posterior to the iris.
 - c. Avoid crossing the manipulator over the central optical zone of the lens.
 - d. For a toric lens, orient the lens in the position described on the IOD using the manipulator to rotate the lens by the edge, haptic body or footplates.
- 6) Removing the viscoelastic
 - a. Thoroughly remove all viscoelastic by irrigating with BSS through a cannula or using bimanual irrigation and aspiration. Note that inadequate flushing of the viscoelastic from the eye may lead to elevated postoperative IOP.
 - b. Do not irrigate or aspirate directly through the central port of the lens.
 - c. Use slight incisional pressure while irrigating to allow egress of viscoelastic.
- 7) Constricting the pupil
 - a. Ensure that all footplates are posterior to the iris by direct inspection.
 - b. Ensure that lens axis alignment is at the intended position.
 - c. Instill a miotic agent to constrict the pupil.

8) Sealing the incisions

- a. Ensure that the clear corneal incisions and the paracentesis are watertight.

Postoperative Procedures

- An IOP check will be conducted at approximately 1-6 hours after surgery, prior to release of subject.
- Perioperative concomitant medication regimen to be followed is described in the section “**Perioperative Medications**”.
- Ensure all concomitant medications are documented on the subject case report form.

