7.1.2 Secondary Endpoints

Secondary endpoints will be evaluated in all eyes (primary and fellow eyes) using descriptive statistics with comparisons to PMA data for the approved and currently marketed MICL and TMICL devices, where appropriate. The secondary endpoints have no prespecified performance targets.

- Incidence of PI required to treat elevated IOP caused by mechanical pupillary block through Postoperative Visit 5 (Day 147 – 182).
- Distribution of percent ECD losses and the percent of eyes that have ECD <1500 and ECD <1000 through Postoperative Visit 5 (Day 147 – 182).
- Incidence of AEs through Postoperative Visit 5 (Day 147 – 182).

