7.4 Statistical Analysis

The first primary study endpoint is defined as the incidence of PI required to treat elevated IOP caused by mechanical pupillary block through Postoperative Visit 5. The primary analysis will be performed on a minimum of 300 primary eyes that have completed Postoperative Visit 5. Based on complaint data, the SPE rate for secondary PI required to treat elevated IOP caused by mechanical pupillary block is approximately 0.3% for MICTL/TMICTL. Based on the recommended analysis in ISO 11979-7:2018, Annex E, the maximum number of cases allowed before the SPE rate is exceeded for 300 primary eyes of 300 subjects is 3.

The other primary endpoints will be studied using the first treated (i.e., primary) eyes. Secondary endpoints and additional study parameters will be studied using all (primary and fellow) eyes. Data will be summarized with point estimates and exact binomial confidence intervals for binary outcomes such as MRSE within 0.50 D and 1.00 D of target and UDVA 20/40 or better. Continuous outcomes (e.g., %hex, CV) will be described with summary statistics to include N, mean, standard deviation, minimum and maximum, first and third quartiles, and median. Distributions, such as CDVA loss, trabecular pigmentation, PAS, AC cells and flare will be summarized by number and percentage for each visit.

ECD loss over the 1050 – 1170 days of follow up will be modeled using a bi-exponential model with adjustment for correlation between paired eyes. ECD and change in ECD will be summarized at each visit. The number and percentage of eyes with ECD < 1000 and < 1500 will be summarized over time using descriptive statistics.

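### AE incidence is to be compared with parent-lens PMA data without allowing for degree of myopia, which Appendix B says may raise AE rates, so a difference in refraction mix could read as a lens difference.

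*Combined protocol and SAP*

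**What the plan says.** All references are to the combined protocol and SAP.

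- **Comparison.** Section 7.1.2 evaluates the secondary endpoints in primary and fellow eyes "using descriptive statistics with comparisons to PMA data for the approved and currently marketed MICL and TMICL devices, where appropriate". One of them is "Incidence of AEs through Postoperative Visit 5 (Day 147 – 182"). The same section adds: "The secondary endpoints have no prespecified performance targets".
- **Analysis.** Section 7.4 plans point estimates with exact binomial intervals, summary statistics, and counts and percentages by visit. The only adjustment it names is for correlation between paired eyes in the ECD model. It does not stratify or standardise by refraction, and it plans no baseline comparison with the PMA cohort. The Synopsis entry on statistical methods ends in a blacked-out bar, but Section 7.4, which runs parallel to it, shows no redaction.
- **Risk factor.** Appendix B, Precautions: "Subjects with higher degrees of myopia or myopic astigmatism may experience lower efficacy and higher rates of adverse events (AEs) and complications". Appendix B, Warnings, adds a narrower statement: "The long-term risk of visually significant cataract and related secondary surgery may be higher in older subjects and those with higher myopia".
- **Who is enrolled.** Sections 3.2 and 3.2.1 offer consecutive enrolment to eligible subjects from -3.00 to -20.00 D spherical equivalent. The only enrolment limits stated are per site (Section 3.3); none concerns refraction.
- **The formal test.** The PI endpoint in primary eyes has a different reference. Section 7.4: "Based on complaint data, the SPE rate for secondary PI required to treat elevated IOP caused by mechanical pupillary block is approximately 0.3"%.

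**The concern.** The study has no control arm. AE incidence has no performance target, either as a primary endpoint in primary eyes or as a secondary endpoint in all eyes. Apart from the PI rate, the PMA data are the only outside reference named for AEs. With no target and no test, a reader will judge the lens from two rates set side by side.

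The plan itself names degree of myopia as a possible driver of AE rates. If the trial happens to enrol fewer highly myopic eyes than the PMA cohort did, a lens with the same AE rate at every level of myopia will look safer. If it enrols more, the lens will look less safe. A single pooled rate also hides what happened in the more myopic eyes, the group the precaution singles out.

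**Working it through.** **1. The plan's own figures.** Section 7.2 allows at most 3 PI cases in 300 primary eyes at a reference rate of 0.3%. The exact binomial gives P(X ≥ 3) = 0.0626 and P(X ≥ 4) = 0.0133. The significance level is not stated, but one-sided 0.05 and 0.025 both give a limit of 3, so the figure reproduces. The AE detection statement also reproduces: 1 - 0.99^300 = 0.951. Neither figure depends on how the PMA comparison is made.

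**2. What mix alone can do to a crude AE ratio.** The documents give neither the PMA refraction mix nor AE rates by refraction, so the inputs here are assumptions:

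- r = AE rate in highly myopic eyes divided by the rate in other eyes, set at 1.5, 2 and 3;
- h = share of highly myopic eyes in each cohort;
- identical lens, meaning the same AE rate within each refraction group in both cohorts.

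Crude ratio, trial to PMA = [1 + (r - 1) × h_trial] / [1 + (r - 1) × h_PMA].

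| h_PMA | h_trial | r = 1.5 | r = 2 | r = 3 |
|---|---|---|---|---|
| 0.50 | 0.20 | 1.10/1.25 = 0.88 | 1.20/1.50 = 0.80 | 1.40/2.00 = 0.70 |
| 0.20 | 0.50 | 1.25/1.10 = 1.14 | 1.50/1.20 = 1.25 | 2.00/1.40 = 1.43 |
| 0.50 | 0.35 | 1.175/1.25 = 0.94 | 1.35/1.50 = 0.90 | 1.70/2.00 = 0.85 |

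The true ratio is 1.00 in every cell.

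**3. What standardising does.** Take r = 2, h_PMA = 0.50, h_trial = 0.20, and let p be the rate in less myopic eyes. The crude trial rate is 0.8p + 0.2 × 2p = 1.2p. The PMA rate is 0.5p + 0.5 × 2p = 1.5p. Weighting the trial's two group rates by the PMA shares gives 0.5p + 0.5 × 2p = 1.5p, and the ratio returns to 1.00.

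**4. Why PI should stay out of this.** At 0.3% the expected count is 300 × 0.003 = 0.9 in 300 primary eyes, and 666 × 0.003 = 2.0 even if all 333 fellow eyes are added. Refraction bands would be almost all empty.

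**The case against.** The strongest reply is that nothing turns on this comparison. It is secondary, descriptive, made only where appropriate, and has no target. The plan never says the comparison will be crude: stratified tables are also descriptive statistics, so the plan is silent on case mix rather than committed to ignoring it. The precaution says *may*, and the documents show no actual imbalance. All of this stands, and it limits the weight of the point. It does not remove the point: the plan gives no criterion for when a comparison is appropriate, and leaving case mix unmentioned makes a pooled comparison the likely default.

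A reader might also infer more than the documents support:

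- **That the formal PI test is affected.** Its reference is a complaint-data rate, not PMA data, and no passage ties PI or pupillary block specifically to degree of myopia. Even if the assumptions in the first two table rows were applied to it, a 0.3% rate would become 0.21% to 0.43%, and the chance of 4 or more cases in 300 would be 0.4% to 4.1%, against 1.3%.
- **That age confounds the comparison in the same way.** The age warning concerns long-term cataract, while the compared AEs stop at Day 147 to 182.
- **That effectiveness results are affected.** Section 7.1.3 plans no PMA comparison for them.
- **That the ECD entry table proves a different case mix.** The fitted starting ECD for the parent lens in Section 7.2.1 (66.2 + 2591.8 = 2658) clears only 6 of the 15 entry cells for ages 21 to 45. But a fitted mean does not show how many of those subjects would have qualified, the documents do not give the PMA entry criteria, and ECD says nothing about refraction mix.
- **That a full refraction-by-age standardisation should replace the crude rate.** It would be undefined where a trial cell is empty and unstable where cells are small.

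**Conclusion.** The point holds as a gap in a descriptive comparison. The plan names degree of myopia as a possible determinant of AE rates, enrols across -3 to -20 D without a quota, and compares AE incidence with PMA data with no provision for refraction mix. The size and direction of any distortion are unknown. Under assumed rate ratios of 1.5 to 3 and high-myopia shares of 50% and 20%, mix alone moves the ratio for an identical lens to between 0.70 and 1.43; a milder contrast of 50% against 35% gives 0.85 to 0.94. These ranges show what is possible and do not estimate a bias.

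It would be wrong to conclude that the trial's AE comparison is biased, or that its pass/fail result is in doubt. The sample of 300, the enrolment of 333 and the limit of 3 PI cases are untouched. This is a low-cost improvement in how the AE comparison is reported.

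**What to change.** In Sections 7.1.2 and 7.4:

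1. Tabulate preoperative MRSE, cylinder, age and lens type (toric or non-toric) beside the same characteristics of the PMA cohort.
2. Report the common AEs by a few preoperative MRSE bands, including the -15 D cut already used in the Appendix B indications. Give the PMA figure for the same band where available. Fix the other cut points before the AE data are reviewed.
3. Where PMA band counts exist and no trial band is empty, add an AE rate standardised to the PMA MRSE distribution as a supportive figure beside the crude rate. Otherwise, state that the crude comparison is not adjusted for case mix.

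Do not stratify PI, and leave its formal test against the complaint-data rate as it is.

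The cost is SAP wording and extra tables. Refraction and demographics are already collected at the preoperative visit (Appendix A), and the implanted model gives the lens type. The downside is wide intervals in small bands, above all beyond -15 D.
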